3.3 Exploratory Objectives

[figure not shown]
Exploratory objectives will include the assessment of free living activity in subjects on Bavisant compared to placebo after 6 weeks of treatment using a wrist-worn actigraphy.

4 DESIGN OF THE STUDY

This phase 2b study is designed as multicentre, multinational, randomized, double blind, parallel group and placebo controlled with three doses of Bavisant (0.5, 1, and 3 mg/d) in subjects with excessive daytime sleepiness with Parkinson's disease. This study will involve approximately 230

subjects from around 48 sites globally. Eligible subjects will be randomly allocated at a ratio of 1:1:1:1 to either Bavisant (at doses of 0.5, 1 and 3 mg/d) or placebo. After signing the study informed consent, subjects meeting the UK PDS Brain Bank Clinical Diagnostic Criteria for Parkinson's disease (see details in the protocol Appendix 18.2) will enter a screening period (lasting up to 3 weeks) followed by a baseline period (lasting up to 1 week). Key inclusion / exclusion criteria will be verified to determine subject eligibility at the screening, baseline periods and prior to randomisation, including the suicide risk assessment following the FDA Guidance for Industry on Suicidal Ideation and Behavior. There is a 6 weeks treatment period, starting on Day 1, followed by a safety follow-up at least 4 weeks after completion of the treatment period. Additional unscheduled visits may be required based on the investigators' judgement at the end of study visit or at the safety follow-up. For early termination, all the assessments of the treatment week 6 visit should be performed, if possible, including the safety follow-up 4 weeks after the last investigational medicinal product (IMP) administration. The figure below describes the study flow graphically.

Figure 1

4.1 STUDY WINDOWS

The process described here will be applied for visit re-allocation except any other approach was described in section 10 or 13 of this SAP for the corresponding statistical analysis. No re-allocation will be performed for nominal visits already provided in the clinical database (visit 1, visit 2 and visit 3). However, unscheduled visits or Early Termination visit may be used to complete any missing information not gathered in the scheduled visit 2 and visit 3, according to the table below.

Table 1: Reallocation time windows definition

Scheduled Visit Post-baseline	Target Study Day	Analysis window in study days
Visit 2 (week 2)	14	10 to 21
Visit 3 (week 6)	42	22 to 45

Unscheduled visits occurring outside of the analysis windows will not be re-allocated.

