#### 6.2. Endpoints

#### **6.2.1** Primary Endpoint

The primary endpoint will be the mean absolute change of Bavisant treatment groups in the Epworth Sleepiness Scale (ESS) from baseline to the end of the 6-week treatment period, assessed as both the intragroup change compared to baseline and intergroup change compared to placebo.

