# Treatment Visit 3 (Day 42 ±3)

This visit will be performed 6 weeks after the 1st treatment administration (Day 1). The following examinations/procedures will be performed:

- Physical examination
- Vital signs
- Laboratory (haematology, biochemistry), serum pregnancy test (for women of childbearing potential)
- Electrocardiogram, heart rate, blood pressure
- Assessment of sleepiness scales: ESS, SCOPA-Sleep, PDSS-2
- Maintenance of Wakefulness Test (MWT)

Protocol No.: BB-2001-201b EudraCT No.: 2017-000877-35 Amendment 04, Final Version 1.0 07/Nov/2018 Page 61 / 142

- Polysomnography
- Cognitive assessment (MoCA)
- Columbia-Suicide Severity Rating Scale (C-SSRS)
- Fatigue assessment (FSS)
- Other scales: UPDRS Part III, HAM-D and BPRS+
- Wrist-worn actigraphy assessment 7 days continuously **before** last dose (day 35 to day 42).
- Wrist-worn actigraphy device return
- Drug return and accountability
- Recording of adverse events
- Recording of concomitant medication
- Eye examination (should be performed after the last treatment on Day 42 and before the follow up safety call)

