#### 11.1.3 Efficacy Analyses

# 11.1.4 Primary Efficacy Analyses

ESS mean absolute change from baseline to the end of the 6-week treatment period will be analysed with an ANCOVA model, with the baseline ESS as a covariate, region and treatment as a factor. Missing data in the 6-week ESS evaluation will be considered as a treatment failure, that is imputing the missing ESS reduction as 0. Least-squared (LS) absolute mean changes will be presented by treatment group together with their corresponding 95% confidence interval. Paired-comparisons will be performed without any multiplicity adjustment.

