# 11.5. Handling of dropouts or missing data

For the primary analysis ESS missing at 6-weeks will be inputed under the treatment failure approach.

As sensitivity analyses, a mixed-effect model with repeated measures (MMRM) approach will be used, under the missing at random framework carried out using an adequate contrast at Week 2 or Week 6, accordingly. The model will include fixed categorical effects of treatment group, visit and treatment-by-visit interaction as well as the continuous fixed covariates of mean baseline ESS. This MMRM model will be run with an unstructured correlation matrix to model the within-subject errors.

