9.1 Primary Endpoint for Efficacy

ESS mean absolute change from baseline to the end of the 6-week treatment period will be defined as the Total ESS score at visit 3 – Baseline ESS score. ESS questionnaire consists of 8 questions which subjects are asked to rate their usual chances of dozing off or falling asleep while engaged in eight different activities. The answers will be provided on a 4-point scale: 0=' would never doze', 1=' slight chance of dozing', 2=' moderate chance of dozing', or 3=' high chance of dozing'. Total ES is the sum of the entries for all of the 8 items-questions. If one or more item-scores are missing, it would not be imputed and this ESS total score will be considered invalid. When ESS was missing in some scheduled post-baseline visit (visit 2 or visit 3) any other ESS total score measured in whether an unscheduled visit or in the early termination visit will be considered according to the re-allocation windows rules presented in section 4.1. Remaining missing for baseline ESS will be imputed to the baseline average, and remaining post-baseline evaluations will be considered as treatment failure, a Multiple Imputation Jumping to Reference Approach will be used (see section 10.4.2 for reference). Negative absolute change will mean improvement.

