10.1.6 Primary Analysis with new missing data allocation windows

The primary analysis will be repeated but considering now the windows below to reallocate missing data:

- Visit 2: 7 to 21 days
- Visit 3: 35 to 49 days

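### SAP 4.1 lets an Early Termination ESS from as early as Day 22 serve as the week-6 value in the primary analysis, ahead of the treatment-failure imputation

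*SAP*

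**What the plan says.** The protocol defines the primary endpoint (6.2.1) as the change in ESS "from baseline to the end of the 6-week treatment period". Protocol 8.4.2 schedules Visit 3 for Day 42 ±3, that is Day 39 to 45.

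SAP 4.1 provides that "unscheduled visits or Early Termination visit may be used to complete any missing information not gathered in the scheduled visit 2 and visit 3". Its Table 1 sets the windows at Day 10 to 21 for Visit 2 and Day 22 to 45 for Visit 3. SAP 9.1 carries this into the primary endpoint: when a scheduled ESS is missing, "any other ESS total score measured in whether an unscheduled visit or in the early termination visit will be considered" under those windows. Only afterwards does the failure rule act: "remaining post-baseline evaluations will be considered as treatment failure, a Multiple Imputation Jumping to Reference Approach will be used".

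The protocol's failure rule is in 11.1.4 ("Missing data in the 6-week ESS evaluation will be considered as a treatment failure, that is imputing the missing ESS reduction as 0") and again in 11.5 ("For the primary analysis ESS missing at 6-weeks will be inputed under the treatment failure approach"). In the SAP, zero reduction is a sensitivity analysis (10.1.1), and jump-to-reference multiple imputation is the primary rule.

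SAP 10.1.6 repeats the primary analysis with other windows, including "Visit 3: 35 to 49 days".

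**The concern.** Re-allocation comes before imputation, so the calendar day of the Early Termination visit decides how a withdrawal is treated. A visit on Day 21 can fill only Visit 2. Visit 3 then stays missing and is imputed as failure. A visit on Day 22 fills Visit 3 and enters the ANCOVA as observed 6-week data. The two subjects differ by one day and neither was observed near six weeks.

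The primary estimate then mixes effects at week 6 with effects from about week 3 onward in subjects who did not complete treatment. Jump-to-reference gives active-arm withdrawals a placebo-like mean. Accepting an earlier observed value instead can retain active-arm benefit that this imputation would remove, whereas placebo withdrawals have no such benefit to retain. The effect therefore need not cancel between arms.

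**Working it through.** The plan states no figure for the effect of this rule, so there is none to reproduce. The check is day arithmetic followed by a scaled illustration.

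**Window, from SAP 4.1 Table 1 and Protocol 8.4.2**
- Length: 45 − 22 + 1 = 24 days.
- Reach around the target: 42 − 22 = 20 days before and 45 − 42 = 3 days after.
- Distance from the earliest protocol Visit 3 day: 39 − 22 = 17 days.
- Days accepted by the SAP but earlier than the protocol's Visit 3 window: Day 22 to 38, which is 17 days. Days 39 to 41 lie within the protocol window and are not counted against the plan.

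**Inputs for scale**
- From the documents: 230 randomised 1:1:1:1, so 230/4 = 57.5 per arm; withdrawal around 15%; planned difference 3.0; SD 5.0.
- Assumed: withdrawals uniform over Day 1 to 41, all Early Termination visits attended on the day of withdrawal, and affected active-arm subjects keeping the full 3.0-point advantage. The documents give no withdrawal timing.

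**Subjects affected**
- Withdrawals per arm: 57.5 × 0.15 = 8.6.
- Share on Day 22 to 38: 17/41 = 0.415.
- Number: 8.6 × 0.415 = 3.6 per arm, or 0.15 × 0.415 = 6.2% of an arm.

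**Shift in the between-arm difference**
- Fraction of the arm × retained advantage: 0.15 × 0.415 × 3.0 = 0.19 points.
- Relative to the planned difference: 0.19/3.0 = 6%.
- Relative to the standard error: 5.0 × √(2/57.5) = 0.93, and 0.19/0.93 is about 0.2 standard errors.

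**Range.** Let withdrawal run from 10% to 20% and the share on Day 22 to 38 from 25% to 60%:
- Low: 0.10 × 0.25 × 3.0 = 0.08 points; 230 × 0.10 × 0.25 = about 6 subjects in the trial.
- High: 0.20 × 0.60 × 3.0 = 0.36 points; 230 × 0.20 × 0.60 = about 28 subjects.

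**What the Day 35 to 49 window would change**
- Visits on Day 22 to 34 (13 days) return to imputation: 13/41 = 0.317, and 8.6 × 0.317 = 2.7 per arm.
- Corresponding shift: 0.15 × 0.317 × 3.0 = 0.14 points.
- Visits on Day 35 to 38 (4 days) are still accepted: 8.6 × 4/41 = 0.8 per arm.

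**The case against.** **The protocol pairs the two visits.** Section 8.4.1.14.1 lists the ESS at Visit 3 or early termination, the schedule in 18.15 has one combined column for them, and 8.4.2 asks for the Visit 3 procedures at early termination. The protocol nowhere says that an Early Termination ESS leaves week 6 missing. A reader might infer that the SAP overrides the protocol's failure rule. That is not established, because the failure rule covers missing 6-week values and the protocol can be read as counting the Early Termination ESS as present. On that reading the SAP even narrows the protocol by refusing values before Day 22. It remains true that a Day 22 score does not measure a 6-week effect.

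**It is not last observation carried forward for all late withdrawals.** A reader might infer this for everyone who leaves from Day 22. A subject without an Early Termination ESS does not have the Day 14 score carried forward; that subject is imputed by jump-to-reference. Protocol 7.1 asks for the early termination assessments only where possible, so full attendance gives an upper figure.

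**It does not concern Early Termination visits alone.** The unscheduled-visit list in Protocol 8.4.2 omits the ESS but is worded as optional, and SAP 9.1 expressly allows for an unscheduled ESS. Early Termination is the main route, not the only one.

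**The direction of bias is open.** A reader might infer that the rule favours the drug, or a poorly tolerated dose. Subjects who leave for lack of effect bring poor observed scores, which the narrower window would replace with placebo-like ones; that would flatter the drug. Protocol 5.2 reports dose-related adverse events such as insomnia and nausea, but 7.2 says that the rates at 1 and 3 mg were below those at 10 mg. Differential withdrawal is possible, not shown. Nor is the score necessarily on-drug, since the window follows visit day and not last dose.

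**The sponsor already plans the narrower window.** This is the strongest point against urgency. However, SAP 10.1.6 leaves the primary estimate unchanged, and the zero-reduction analysis in 10.1.1 states no window of its own and so inherits Day 22 to 45.

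**Conclusion.** The point holds as a matter of endpoint definition. The primary analysis accepts as week-6 data a score taken up to 17 days before the protocol's earliest Visit 3 day, and it treats otherwise similar withdrawals differently on either side of Day 21/22. The illustrative effect is about 0.19 points (0.08 to 0.36 over the range shown) against a planned 3.0. It rests on assumed withdrawal timing, full attendance and a fully retained advantage. The sign cannot be fixed from the documents. The change is worth making because it is inexpensive and brings the primary analysis closer to its stated endpoint; the size of the effect alone would not demand it.

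One related uncertainty remains. SAP 4.1 does not re-allocate nominal visits, and the schedule combines Visit 3 with Early Termination. If Early Termination data are stored under the Visit 3 label, scores from before Day 22 could also count as week 6. The documents do not say how they are labelled.

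**What to change.** In SAP 4.1 and 9.1:
- Use the Day 35 to 49 Visit 3 window of SAP 10.1.6 for the primary analysis and for the zero-reduction analysis in 10.1.1.
- Treat an Early Termination ESS before Day 35 as missing at week 6, so that the SAP's jump-to-reference imputation applies in the primary analysis.
- Keep Day 22 to 45 as the sensitivity analysis.
- State that Early Termination data recorded under the combined Visit 3 column are windowed by actual study day.

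The cost is mainly SAP wording, since the primary analysis is already planned under both windows; only 10.1.1 has to be run under the new one. On the assumptions above, about 2.7 more values per arm are imputed instead of observed. Because the last planned dose is on Day 42 (18.15, note 12), a re-allocated ESS may also come up to 49 − 42 = 7 days after it.

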5 SAMPLE SIZE AND POWER ESTIMATION

A total of 200 completed subjects will be evaluated for the study (50 completed subjects per treatment group, with expected early withdrawal rate of around 15%).

The assumptions used for the sample size calculation are a mean absolute change in the Epworth Sleepiness Scale (ESS) from baseline to the end of the 6-week treatment period of at least 3.0 points (minimum change considered as clinically relevant) and a standard deviation of 5.0 (based on a comparable study of Modafinil in a similar population recruited at one centre (3) which showed a standard deviation in the ESS between 3.5 at baseline and 4.8 at the end of the treatment period) and a reduction in ESS of 2.7 points for subjects treated with Modafinil.

The confirmation of the hypothesis of detecting a mean difference in ESS of 3.0 points vs. baseline requires a sample size of 25 subjects per group (intragroup $\Delta=3.0$; $SD=5.0$; two-side $\alpha=0.05$; $\beta=0.20$; power=80%; one-sample t-test).

The additional endpoint of showing a statistically significant difference of at least 3.0 points in ESS between Bavisant and placebo requires a sample size of 50 subjects per group (between treatment $\Delta=3.0$; $SD=5.0$; two-side $\alpha=0.05$; $\beta=0.20$; power=80%; two-sample equal-variance t-test).

The effect size of Bavisant in EDS is unknown and smaller changes in ESS may be clinically useful according to its profile, and higher variability is expected in this multicentre study; so the sample size of 200 completed subjects (50 per treatment group) is proposed in order to cover both the confirmation of an intragroup change of at least 3.0 points vs. baseline, and the between-group difference of at least 3.0 points change vs. placebo.

The Maintenance of Wakefulness Test (MWT) will be performed in a minimum of 20 subjects per group (80 overall) in order to be enough to show statistically significant differences if the expected MWT absolute change from baseline differs at least in one standard deviation (effect size = 1.0).

6 ANALYSIS SETS

The safety population (SAF) will be defined as all subjects who have received at least one dose of the study treatment.

Sponsor BenevolentAI Bio

Project Code ... BB-2001-201b

The intent to treat population (ITT) will be defined as all randomized subjects who have taken at least one dose of study treatment.

The per protocol population (PP) will be defined as all subjects in the FAS who do not experience a major protocol deviation.

Protocol deviations will be defined as deviations from the procedure outlined in the protocol. Protocol deviations will be identified for each patient in the Data (blind) Review & Evaluability Determination meeting will be held prior to the treatment unblinding. They will be assessed as “minor” or “major” according to the possible impact expected on efficacy results. Minor and major protocol deviations will be fully documented in the Protocol Deviation Document prior to unblinding. Specific data sets will be produced and transferred to Biostatistics department in order to allow the appropriate definition for the Per Protocol Population.

Since the reasons for excluding patients from the analysis cannot be entirely foreseen at the time of writing the statistical analysis plan evolving trial conduct may require some further definition of patients to be excluded, at the end of the trial, but prior to unblinding.

Aspects to be considered (but not limited to) when determining the evaluability of data are as follows:

- Inclusion and exclusion criteria
- Acceptable timings for visit dates and measurements
- Compliance with treatment
- Incorrect randomization/treatment
- Concomitant therapies

As far as possible ITT principle will be guaranteed so it is not expected to have protocol deviations excluding patients from the ITT population.

7 PRESENTATION OF DATA

Tables and listings will be produced in accordance with the principles outlined by the ICH E3 guideline.

Categorical data will be summarized with absolute and relative frequencies (percentage), missing data will not be considered in the percentage calculation, and numerical data will be summarized with the number, mean, median, standard deviation (SD), the range (minimum and maximum), and the first, third quartiles and 95% confidence interval (if applicable). Throughout the presentation of the study results the four treatment groups will be displayed separately. For safety a new column summarizing data for the three active treatment arms together will be added.

8 SOFTWARE

All statistical analyses, listing, tabulations and figures will be producing using SAS® Version 9.4 or higher.

9 EFFICACY ENDPOINTS

Baseline efficacy value will be defined as the last measure done prior to the randomization.

9.1 Primary Endpoint for Efficacy

ESS mean absolute change from baseline to the end of the 6-week treatment period will be defined as the Total ESS score at visit 3 – Baseline ESS score. ESS questionnaire consists of 8 questions which subjects are asked to rate their usual chances of dozing off or falling asleep while engaged in eight different activities. The answers will be provided on a 4-point scale: 0=' would never doze', 1=' slight chance of dozing', 2=' moderate chance of dozing', or 3=' high chance of dozing'. Total ES is the sum of the entries for all of the 8 items-questions. If one or more item-scores are missing, it would not be imputed and this ESS total score will be considered invalid. When ESS was missing in some scheduled post-baseline visit (visit 2 or visit 3) any other ESS total score measured in whether an unscheduled visit or in the early termination visit will be considered according to the re-allocation windows rules presented in section 4.1. Remaining missing for baseline ESS will be imputed to the baseline average, and remaining post-baseline evaluations will be considered as treatment failure, a Multiple Imputation Jumping to Reference Approach will be used (see section 10.4.2 for reference). Negative absolute change will mean improvement.

9.2 Secondary Endpoints for Efficacy

9.2.1 Epworth Sleepiness Scale (ESS)

- ESS mean absolute change from baseline to the end of the 2-week treatment will be defined as Total ESS score at visit 2 – Baseline ESS score.
- ESS clinical response, defined as:
 - o First approach: ESS absolute decrease from baseline of at least 3.0 points, after 2 and 6 weeks of treatment.
 - o Second approach: $ESS \leq 10$ after 2 and 6 weeks of treatment.
 - o Third approach: Either $ESS \leq 10$ after 2 and 6 weeks of treatment or ESS absolute decrease from baseline of at least 3.0 points after 2 and 6 weeks of treatment.
- Mean relative change in the ESS from baseline to the end of the 2-week and 6-week treatment periods (percentage of absolute decrease compared to baseline ESS). For each patients the relative change will be calculates as:

Relative change: $(\text{post-baseline evaluation} - \text{baseline evaluation}) / \text{baseline evaluation}$

The same missing imputation strategy as used for primary endpoint will be used for the ESS secondary endpoints (see section 9.1 and 10.4.2 for reference).

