10 STATISTICAL METHODOLOGY FOR EFFICACY ENDPOINTS

10.1 Primary Efficacy Analysis

ESS mean absolute change from baseline to the end of the 6-week treatment period will be analysed with an ANCOVA model, with the baseline ESS as a covariate, region and treatment as a factor. Least-squared (LS) absolute mean changes will be presented by treatment group along with their associated 95% CIs and 2sided p-values; these data will then provide estimated for the within arm change from baseline. The difference between each of the 3 dose arms and the placebo arms in Least-squared (LS) absolute mean changes will also be presented together with the corresponding 95% confidence interval and 2-sided p-value. These paired comparisons will be performed without any multiplicity adjustment. Also, the 4 degrees of freedom (DF) associated with the overall F-test for differences between the treatment arms will be decomposed using Type I sums of squares into three orthogonal single DF contrasts to estimate the linear, quadratic and cubic components of any potential dose response. Baseline data will be imputed with the baseline ESS average. Multiple Imputation Jumping to Reference method will be used to impute post-baseline data (see section 10.4.2 for further reference).

10.1.1 Sensitivity analyses missing reductions imputed to 0:

Same primary analysis will be repeated imputing post-baseline missing ESS evaluations to baseline data that is reduction equal to 0.

10.1.2 Sensitivity analyses MMRM Model:

A mixed-effect model with repeated measures (MMRM) approach will be used, under the missing at random framework carried out using an adequate contrast at Week 2 or Week 6, accordingly. The model will include fixed categorical effects of treatment group, region, visit and treatment-by-visit interaction as well as the continuous fixed covariates of mean baseline ESS. This MMRM model will be run with an unstructured correlation matrix to model the within subject errors. In this case missing values will not be imputed, since (MMRM) is handling missing data through the Maximum Likelihood estimation method.

Unstructured covariance matrix is assumed to explain within subject covariance in MMRM method in protecting the type I error rates. In the event if the assumption of unstructured covariance (UN) matrix results in non-convergence of the model, only then the following covariance structures will be considered in the order mentioned below.

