10.2 Secondary Efficacy Analysis

All secondary endpoints evaluated through a mean absolute change will follow a similar statistical analysis as for the primary variable (ANCOVA, considering baseline corresponding endpoint evaluation as covariate and treatment and region as fixed factors):

- Mean changes of ESS (up to 2-week treatment period)
- Mean relative change in the Epworth Sleepiness Scale (ESS) from baseline to the end of the 2-week and 6-week treatment periods (percentage of absolute decrease compared to baseline ESS).
- SCOPA-Sleep (up to 2-week and 6-week treatment period)
- PDSS-2 (2-week and 6-week)
- MWT (6-week)
- Polysomnography (6-week)
 - o Sleep Efficiency
 - o Percentage of TST REM
- UPDRS Part III (2-week and 6-week)
- Motor function assessed by the wrist worn device (6-week)
- HAM-D (2-week, 6-week and follow-up)
- MoCA (6-week), and FSS (6-week).
- Fatigue Severity scale (FSS)
- Polysomnography (6-week): Baseline index will not be considered in these Logistic models.
 - o Events Index (Increase in Events Index)
 - o Arousal Index (Increase in Arousal Index)

Categorical variables as detailed below will be analysed through fitted logistic regression model adjusted on baseline corresponding endpoint evaluation as a covariate and treatment and region as fixed factors. This model will estimate the adjusted Odds Ratio between treatment arms, its corresponding 95% and P-value.

- ESS clinical response, defined as ESS absolute decrease from baseline of at least 3.0 points, after 2 and 6 weeks of treatment.
- ESS clinical response, defined as $ESS \leq 10$ after 2 and 6 weeks of treatment.
- ESS clinical response, defined as either $ESS \leq 10$ after 2 and 6 weeks of treatment or ESS absolute decrease from baseline of at least 3.0 points after 2 and 6 weeks of treatment.

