10.4.2 Handling of missing data

- For primary analysis, as describes in section 9.1, post-baseline ESS will be imputed through a Multiple Imputation Jumping to Reference Model.

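### Jump-to-reference imputation lets some subjects the SAP labels treatment failures count as ESS clinical responders, and no planned analysis shows the effect

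*SAP*

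**What the plan says.** SAP 9.1 deals with a missing post-baseline ESS in two steps. First, an ESS from an early termination or unscheduled visit is used if it falls in the SAP 4.1 window (days 10 to 21 for visit 2, days 22 to 45 for visit 3). For what is still missing, "remaining post-baseline evaluations will be considered as treatment failure, a Multiple Imputation Jumping to Reference Approach will be used". SAP 10.4.2 restates the method for the primary analysis: "post-baseline ESS will be imputed through a Multiple Imputation Jumping to Reference Model". It gives no separate rule for binary endpoints.

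SAP 9.2.1 then defines clinical response in three ways, each at weeks 2 and 6: "ESS absolute decrease from baseline of at least 3.0 points, after 2 and 6 weeks of treatment"; ESS of 10 or less; or either of these. It closes with "The same missing imputation strategy as used for primary endpoint will be used for the ESS secondary endpoints".

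SAP 10.2 sets the analysis: "Categorical variables as detailed below will be analysed through fitted logistic regression model adjusted on baseline corresponding endpoint evaluation", with treatment and region as factors and odds ratios as output. It does not mention scoring missing subjects as non-responders.

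The SAP also plans a zero-reduction check in 10.1.1: "Same primary analysis will be repeated imputing post-baseline missing ESS evaluations to baseline data that is reduction equal to 0". Protocol 11.1.4 gives failure that same meaning for the primary analysis: "Missing data in the 6-week ESS evaluation will be considered as a treatment failure, that is imputing the missing ESS reduction as 0".

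**The concern.** The label and the method pull apart once the endpoint is yes/no. For a mean change, jump-to-reference can fairly be described as giving a withdrawn subject no drug benefit beyond placebo. For a response endpoint, the imputed score is compared with a cut-off, and a placebo-like score will often pass it. A subject the plan has just called a treatment failure is then counted as a clinical response in a share of the imputations.

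Two things are at stake. The response percentages in each arm would not mean what a reader of the failure label would expect. And if one dose loses more subjects than placebo, those subjects still earn placebo-like credit on the endpoint meant to show individual benefit. In a dose-finding trial that bears on how the doses are compared. No other analysis of the response endpoints is planned: the zero-reduction analysis (10.1.1), the alternative-window analysis (10.1.6) and the per-protocol repeat (9.4) are all defined for the primary analysis.

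**Working it through.** The documents state no expected response rate and no power for the response endpoints, so there is no plan figure to reproduce.

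**Inputs from the documents**
- SD of ESS 5.0 and a 3.0-point advantage over placebo (SAP 5), with the SD applied here to the change from baseline.
- Withdrawal about 15% (SAP 5) and 230 randomised 1:1:1:1 (SAP 4). So 0.15 x 230 = 34.5 withdrawals, and 34.5 / 4 = 8.6 per arm of 57.5.

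**Assumed input:** placebo mean change m from 0 to -3, because the documents give none.

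**Step 1. Share of placebo-like draws that pass the 3-point criterion.** P(change <= -3) = Phi((-3 - m)/5), with draws taken as continuous. At m = 0 this is Phi(-0.6) = 27.4%; at m = -3 it is Phi(0) = 50.0%. Across the SD range in protocol 7.2 (4.0 to 5.3), the m = 0 figure runs from Phi(-0.75) = 22.7% to Phi(-0.566) = 28.6%.

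**Step 2. Upper bound on the count.** If every withdrawal lacked a usable ESS, then 34.5 x 0.274 = 9.5 to 34.5 x 0.500 = 17.3 subjects trial-wide would be scored as responders on average, or 2.4 to 4.3 per arm. Under failure-as-non-response the count is 0.

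**Step 3. Response rates.** Let pA and pP be the active and placebo response rates with complete data, and d the missing share. On a dose, jump-to-reference gives (1-d)pA + d pP; on placebo it gives pP. Non-response gives (1-d)pA and (1-d)pP. With d = 15% the gap in each arm is 0.15 x pP, which is 4.1 to 7.5 points. Jump-to-reference is written J2R below.

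| m | pP | pA | Active arm, d = 15%: J2R / non-response | Risk difference, 15% both arms: either rule | Risk difference, 25% dose and 10% placebo: J2R / non-response |
|---|---|---|---|---|---|
| 0 | 27.4% | 50.0% | 46.6% / 42.5% | 19.2 | 16.9 / 12.8 |
| -1 | 34.5% | 57.9% | 54.4% / 49.2% | 19.9 | 17.6 / 12.4 |
| -2 | 42.1% | 65.5% | 62.0% / 55.7% | 19.9 | 17.6 / 11.3 |
| -3 | 50.0% | 72.6% | 69.2% / 61.7% | 19.2 | 16.9 / 9.4 |

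The 25%/10% split is illustrative; the documents give no split by arm.

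**Step 4. A second illustration**, with completer response assumed at 40% on placebo and 55% on a dose and missingness at 10% and 25%:
- Jump-to-reference: (0.75 x 0.55 + 0.25 x 0.40) - 0.40 = 11.3 points.
- Non-response: 0.75 x 0.55 - 0.90 x 0.40 = 5.3 points.
- With 15% missing in both arms, both rules give 0.85 x (0.55 - 0.40) = 12.8 points.

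**Step 5. Is the placebo rate the right figure?** A simulation with 400,000 subjects per arm assumed a week-2/week-6 correlation of 0.6 and no usable week-2 score in 40% of those missing. With missingness unrelated to the week-2 score, the imputed response rate matched placebo (27.4% to 50.2%). When worse week-2 scorers dropped out more often, it was 18% to 38%: below placebo, but well above zero. The actual figure depends on the imputation model, which the SAP does not spell out.

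**Step 6. The ESS of 10 or less criterion.** With an assumed baseline of mean 16 and SD 2.5, limited to whole scores of 13 to 24, the imputed response rate was 13% to 29% with missingness unrelated to week 2. Zero reduction gives 0% for any baseline above 10. Entry requires a screening ESS above 12 (protocol 8.1), so nearly all subjects should be in that position.

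**The case against.** The strongest reply is that this is a choice of estimand. Cutting jump-to-reference draws at a threshold is a recognised method, and SAP 9.1 gives treatment failure its working meaning in the same sentence. On that view nothing is inflated, because non-response is not the truth against which the result should be measured. This stands in part: the method is legitimate in itself, and any excess is measured only against the plan's own failure label.

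Three stronger readings are tempting, and the documents do not support them.

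- A reader might infer that the SAP contradicts a protocol rule for the response endpoints. Protocol 11.1.4 writes the zero-reduction rule for the primary mean change. Protocol 11.1.5 extends the primary methodology only to secondary variables measured as mean changes, and its response paragraph has no imputation rule. The protocol's general convention (11.1) leaves missing values out of percentages.
- A reader might infer that every withdrawn subject is imputed. Protocol 8.4.2 and 8.5.2 ask for the week-6 procedures at early termination, and an ESS on days 22 to 45 then fills visit 3. One on days 10 to 21 fills only visit 2, so week 6 is still imputed. Subjects who leave after visit 2 already have a week-2 score. The counts and percentage-point gaps in steps 2 and 3 are therefore upper bounds.
- A reader might infer that the treatment effect is biased towards the drug. With equal missingness the risk difference does not move. The odds ratio, which SAP 10.2 actually plans, is then slightly less favourable to the drug. At 15% missing and 40%/55% completer response it is (0.5275/0.4725)/(0.40/0.60) = 1.68 under jump-to-reference and (0.4675/0.5325)/(0.34/0.66) = 1.70 under non-response. Any advantage for a dose needs excess missingness on that dose, which is assumed here.

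**Conclusion.** The point holds as an internal inconsistency in the SAP with no planned check. Subjects whose ESS is still missing after re-allocation are called failures, but some are scored as clinical responders, at up to about the placebo response rate. On the 3-point criterion that is 27% to 50%, assuming a placebo change of 0 to -3 and SD 5.0, and lower if subjects with worse week-2 scores drop out. The effect on an arm's response rate is at most about 4 to 7.5 points, reached only if all 15% withdrawals lack a usable ESS. The contrast between arms is affected materially only if missingness differs; the 11.3 against 5.3 points shows the direction and possible scale, not an expected value. These are secondary endpoints without multiplicity control, so this is a worthwhile low-cost improvement and not a threat to the primary analysis.

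**What to change.** In SAP 9.2.1 and 10.4.2, state that for the three response definitions a subject whose week-2 or week-6 ESS is still missing after re-allocation is a non-responder for that visit. Apply this for any reason, including a missed visit or a total made invalid by a missing item, so that no second rule is needed. Keep the jump-to-reference version as a sensitivity analysis.

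At a minimum, extend the 10.1.1 zero-reduction analysis to the three response endpoints and report both results. The two options differ only for a subject whose baseline ESS is already 10 or less: zero reduction would still count that subject as a responder on the second and third definitions.

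The cost is a sentence or two before unblinding, a little extra programming, and slightly lower stated response rates. No new data are needed.
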